6.4 Supportive Care during Transplant

On the day of admission menstruating females will start Provera 10mg p.o. daily and Nystatin vaginal suppositories 1 b.i.d. In addition, all patients will start, levofloxacin 500mg/p.o or I/V q daily, Bactrim DS 1 tablet p.o. b.i.d. or IV will be started and continue until day -2.

Hyperalimentation will be given while patient is unable to eat.

It is recommended that platelet transfusions will be given to maintain platelet count greater than 20,000/ μ l at all times. Single donor platelets will be used with an attempt to use family members when possible. All platelets will be filtered to remove contaminated leukocytes which may harbor cytomegalovirus (CMV). Packed RBC transfusions will be used to keep the hemoglobin greater than 8.5gm/dl. All blood products will be irradiated with 2500cGy prior to transfusions.

The management of infections in these immunocompromised patients must by necessity be individualized, but the following general approach will be utilized. If a specific infection is documented, patients will be placed on specific anti-microbial agents to treat that infection. For temperatures greater than 38.5°C without an obvious source in patients with less than 1000granulocytes/l, cultures of blood will be obtained. Following this, a third generation cephalosporin will be used as initial empiric antibiotic coverage. For persistent or recurrent fevers an aminoglycoside and or ancef will be added. Prophylactic intravenous amphotericin B will be used and the dose can be increased as clinically indicated. If a specific organism or site of infection is identified after starting empiric antibiotic coverage, therapy will be changed as needed.

Rev. 11/8/01

While hospitalized, patients will have daily CBC's with platelet count, and SMA-7 (Na, K, C1, CO₂, BUN, creatinine, glucose). SMA12 (total protein, albumin, phosphatase, Ca, SGPT, SGOT, alkaline phosphatase, total bilirubin, cholesterol) determinations will be performed on Monday, Wednesday and Fridays and chest x-rays will be done weekly. CSA levels q Mon & Thurs, and CMV blood cultures q Mon & Thurs when WBC >2000.

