10.0 CRITERIA FOR EVALUATION AND DEFINITION

- 10.1 Achievement of a lymphohematopoietic graft is defined as recovery from post-transplant.
- 10.2 Complete remission is defined as attainment of M-1 marrow status, and no evidence of recurrent extramedullary disease.
- 10.3 Length of survival is measured from entry on study to death or time of last contact.
- 10.4 Treatment failure is defined as death from toxicities associated with transplant procedure or recurrence of malignancy.
- 10.5 All registered patients including those removed from the treatment protocol will be followed for survival every six months.

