12.0 STATISTICAL CONSIDERATIONS

- 12.1 Primary and Secondary Endpoints: The primary endpoint of the Phase II study is to evaluate the efficacy of FTBI/BU/VP-16 with a targeted Busulfan dose of AUC 700-900 as a preparative regimen for allogeneic BMT in patients with advanced hematological malignancies (AML or ALL beyond second remission, in induction

failure, or in relapse; CML in blast crisis; and myelodysplasia, RAEB and RAEBIT). Secondary endpoints will include early and late toxicities of this regimen.

Efficacy will be estimated based on 2 and 5 year disease-free survival (DFS). The effects of cytogenetics, WBC at presentation, and number of courses of induction therapy to achieve remission will be evaluated as possible prognostic factors for relapse, DFS, and overall survival.

- 12.2 Sample size Estimation and Length of Accrual: A total of 50 patients with advanced malignancies and less than 50 years old (physiological age) will be accrued to this trial, so that in estimating the engraftment and relapse rates the maximum standard error will be 0.7. We expect to accrue approximately 10-12 patients per year so that this trial will require 4-5 years of completion.
- 12.3 If at any time the severe treatment related complication rate (e.g. severe VOD, interstitial pneumonia, neurotoxicity at day 100 post BMT) or regimen related mortality exceeds 20% with a high probability (i.e. >95%) then further accrual to the trial will be terminated. This would occur if the following numbers of events have been observed, monitoring after every set of 10 patients is accrued:

| Number of Patients Accrued | Number of Events Leading to Early Termination |
|-------------------------------|--|
| 10 | 5 |
| 20 | 8 |
| 30 | 11 |
| 40 | 14 |

12.4 **Statistical Analyses:** The rate of engraftment and median time to engraftment will be estimated, defined as time to ANC > 500 and platelets >20,000.

The Kaplan-Meier method will be used to estimate time to relapse, DFS, and overall survival, and 95% confidence intervals will be calculated using Greenwood's variance.

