| For BMT studies, if specified in the protocol | WNL | $\geq 1.0 - <1.5 \times 10^9/L$ $\geq 1000 - <1500/mm^3$ | $\geq 0.5 - <1.0 \times 10^9/L$ $\geq 500 - <1000/mm^3$ | $\geq 0.1 - <0.5 \times 10^9/L$ $\geq 100 - <500/mm^3$ | $<0.1 \times 10^9/L$ $<100/mm^3$ |
| For leukemia studies or bone marrow infiltrative myeloproliferative process, if specified in the protocol | WNL | $10 - <25\% \text{ decrease from baseline}$ | $25 - <50\% \text{ decrease from baseline}$ | $50 - <75\% \text{ decrease from baseline}$ | $>75\% \text{ decrease from baseline}$ |
| Platelets | WNL | $\leq LLN - 75.0 \times 10^9/L$ $\leq LLN - 75,000/mm^3$ | $\geq 50.0 - <75.0 \times 10^9/L$ $\geq 50,000 - <75,000/mm^3$ | $\geq 10.0 - <50.0 \times 10^9/L$ $\geq 10,000 - <50,000/mm^3$ | $<10.0 \times 10^9/L$ $<10,000/mm^3$ |
| For BMT studies, if specified in the protocol | WNL | $\geq 50.0 - <75.0 \times 10^9/L$ $\geq 50,000 - <75,000/mm^3$ | $\geq 20.0 - <50.0 \times 10^9/L$ $\geq 20,000 - <50,000/mm^3$ | $\geq 10.0 - <20.0 \times 10^9/L$ $\geq 10,000 - <20,000/mm^3$ | $<10.0 \times 10^9/L$ $<10,000/mm^3$ |
| For leukemia studies or bone marrow infiltrative myeloproliferative process, if specified in the protocol | WNL | $10 - <25\% \text{ decrease from baseline}$ | $25 - <50\% \text{ decrease from baseline}$ | $50 - <75\% \text{ decrease from baseline}$ | $>75\% \text{ decrease from baseline}$ |
| Transfusion: Platelets | none | - | - | yes | platelet transfusions and other measures required to improve platelet increment; platelet transfusion refractoriness associated with life-threatening bleeding (e.g., HLA or cross matched platelet transfusions) |
| For BMT studies, if specified in the protocol | none | 1 platelet transfusion in 24 hours | 2 platelet transfusions in 24 hours | 23 platelet transfusions in 24 hours | platelet transfusions and other measures required to improve platelet increment; platelet transfusion refractoriness associated with life-threatening bleeding (e.g., HLA or cross matched platelet transfusions) |
| Also consider Platelets. | | | | | |

| Adverse Event | Grade | | | | |
|---|-------------------------------------|--|--|--|--|
| | 0 | 1 | 2 | 3 | 4 |
| Transfusion: pRBCs | none | - | - | yes | - |

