| Rash/dermatitis associated with high-dose chemotherapy or BMT studies. | none | fair erythema or dry desquamation | moderate to brisk erythema or a patchy moist desquamation, mostly confined to skin folds and creases; moderate edema | confluent moist desquamation, ≥1.5 cm diameter, not confined to skin folds; pitting edema | skin necrosis or ulceration of full thickness dermis; may include spontaneous bleeding not induced by minor trauma or abrasion |
| Rash/desquamation associated with graft versus host disease (GVHD) for BMT studies. | none | macular or papular eruption or erythema covering <15% of body surface area without associated symptoms | macular or papular eruption or erythema with pruritis or other associated symptoms covering ≥15 - <50% of body surface or localized desquamation or other lesions covering ≥50% of body surface area | symptomatic generalized erythroderma or symptomatic macular, papular or vesicular eruption, with bullous formation, or desquamation covering ≥50% of body surface area | generalized exfoliative dermatitis or ulcerative dermatitis or bullous formation |

BMT-Specific Adverse Events

Summary of BMT-Specific Adverse Events that may be used if specified by the protocol. These differ from the standard CTC and may be more relevant to the transplant setting. They are listed here for the convenience of investigators writing transplant protocols. They are also included in the CTC document.

| Adverse Event | Grade | | | | |
|--|-------|--|--|--|--|
| | 0 | 1 | 2 | 3 | 4 |
| Stomatitis/pharyngitis (oral/pharyngeal mucositis) for BMT studies. | none | painless ulcers, erythema or mild soreness in the absence of lesions | painful erythema, edema or ulcers but can swallow | painful erythema, edema, or ulcers preventing swallowing or requiring hydration or parenteral (or enteral) nutritional support | severe ulceration requiring prophylactic intubation or resulting in documented aspiration pneumonia |
| Transfusion: Platelets for BMT studies. | none | 1 platelet transfusion in 24 hours | 2 platelet transfusions in 24 hours | ≥3 platelet transfusions in 24 hours | platelet transfusions and other measures required to improve platelet increment; platelet transfusion refractoriness associated with life-threatening bleeding. (e.g., HLA or cross matched platelet transfusions) |

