| Transfusion: pRBCs for BMT studies. | none | ≤1 u pRBC in 24 hours elective or planned | 3 u pRBC in 24 hours elective or planned | ≥4 u pRBC in 24 hours | hemorrhage or hemolysis associated with life-threatening anemia; medical intervention required to improve hemoglobin |
| Transfusion: pRBCs for pediatric BMT studies. | none | ≤15mL/kg in 24 hours elective or planned | >15 - ≤30mL/kg in 24 hours elective or planned | >30mL/kg in 24 hours | hemorrhage or hemolysis associated with life-threatening anemia; medical intervention required to improve hemoglobin |
| Thrombotic microangiopathy (e.g., thrombotic thrombocytopenic purpura/TTP or hemolytic uremic syndrome/HUS) for BMT studies. | | evidence of RBC destruction (schistocytosis) without clinical consequences | evidence of RBC destruction with elevated creatinine (≤ 3 x ULN) | evidence of RBC destruction with creatinine (>3 x ULN) not requiring dialysis | evidence of RBC destruction with renal failure requiring dialysis and/or encephalopathy |
| Weight gain associated with Veno-Occclusive Disease (VOD) for BMT studies. | <2% | ≥2 - <5% | ≥5 - <10% | ≥10% or as ascites | ≥10% or fluid retention resulting in pulmonary failure |

BMT Complex/Multicomponent Events

| Adverse Event | Grade | | | | |
|---|--------|------|----------|--------|------------------|
| | 0 | 1 | 2 | 3 | 4 |
| Note: The grading of Complex/Multicomponent Events in bone marrow transplant will be defined in the protocol. The grading scale must use the CTC criteria for grading the specific component events (adverse events). | | | | | |
| Failure to engraft | absent | mild | moderate | severe | life-threatening |
| Also consider Hemoglobin, Neutrophils/granulocytes (ANC/AGC), Neutrophils/granulocytes (ANC/AGC) for BMT studies, if specified in the protocol. Platelets, Platelets for BMT studies, if specified in the protocol | | | | | |
| Graft versus host disease | absent | mild | moderate | severe | life-threatening |
| Also consider Fatigue, Rash/desquamation, Rash/desquamation associated with graft versus host disease (GVHD) for BMT studies, if specified in the protocol. Diarrhea for patients without colostomy, Diarrhea for patients with colostomy, Diarrhea associated with graft versus host disease (GVHD) for BMT studies, if specified in the protocol, Bilirubin, Bilirubin associated with graft versus host disease (GVHD) for BMT studies, if specified in the protocol | | | | | |

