APPENDIX X

Time points to grade toxicities and collect data.

Day 30 after PBSCT/BMT CTC form.

Day 31 – 100 CTC form and IBMTR booklet.

101 – 365 LT Follow up form.

Every year LT follow up form.

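### Section 12.4 does not require the platelet count above 20,000 to be unsupported, while 6.4 recommends transfusing to keep it above that same value, so the engraftment rate can be too high and the median time too early

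*Combined protocol and SAP*

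**What the plan says.** Section 12.4 opens with engraftment: "The rate of engraftment and median time to engraftment will be estimated", "defined as time to ANC > 500 and platelets >20,000". The definition has two count thresholds. It does not mention transfusion.

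Section 6.4 gives the supportive-care policy: "It is recommended that platelet transfusions will be given to maintain platelet count greater than 20,000" per µl, at all times. The same section has daily blood counts, including platelets, taken while patients are in hospital.

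Four other places bear on the definition:

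- **Section 10.1:** "Achievement of a lymphohematopoietic graft is defined as recovery from post-transplant". The sentence appears incomplete. As it reads, it contains no count and no transfusion rule.
- **Appendix VII, transfusion:** the CTC includes an item "Transfusion: Platelets for BMT studies", which grades how much platelet support a patient needs.
- **Appendix VII, failure to engraft:** this is listed among the complex events, with the note "The grading of Complex/Multicomponent Events in bone marrow transplant will be defined in the protocol". The protocol supplies no such grading.
- **Appendix X:** data collection for days 31 to 100 uses the "CTC form and IBMTR booklet". The contents of the booklet are not reproduced.

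Section 12.2 cites the precision of the engraftment and relapse rates when justifying 50 patients.

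**The concern.** The platelet criterion is meant to show that the graft is producing platelets. A count held above 20,000 by donor platelets does not show that. Because the endpoint threshold and the transfusion target are the same number, a patient supported as 6.4 recommends can pass the platelet part of the definition without any platelet recovery. If 12.4 is read as one joint event, a patient with ANC recovery alone can be recorded as engrafted, and dated at ANC recovery. If it is read as two milestones, the platelet milestone itself can be met by transfusion.

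At stake are the accuracy of the two engraftment summaries and their comparability with any series that used an unsupported count. Two analysts could also date engraftment differently from the same charts, and both could claim to follow the plan.

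**Working it through.** **1. The thresholds side by side.** Endpoint (12.4): platelets > 20,000. Transfusion target (6.4): platelets > 20,000. They are identical. Sections 10.1 and 12.4, the study calendar (Appendix VI), the CTC tables (Appendix VII) and the data schedule (Appendix X) contain no condition that excludes transfused counts.

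**2. Direction.** Let T_A be the day of ANC recovery and T_P the day of unsupported platelet recovery. Under an unsupported definition, joint engraftment occurs at max(T_A, T_P). As written, the platelet part may be met earlier than T_P but never later, and ANC recovery is still required. The as-written date therefore lies between T_A and max(T_A, T_P). The rate can only rise or stay the same, and the median can only fall or stay the same.

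**3. Rate.** The plan states no expected engraftment rate, so there is no figure to reproduce. With n = 50 (12.2), one patient is 1/50 = 2 points. The overstatement cannot exceed 1 − p, where p is the true (unsupported) rate. The rates below are assumed, and SE = √(p(1 − p)/50).

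| Assumed p | Non-engrafted patients | Cap on overstatement | SE | Misclassified patients needed to exceed one SE |
|---|---|---|---|---|
| 0.80 | 10 | 20 points | 5.7 points | 3 of 10 (6 points) |
| 0.90 | 5 | 10 points | 4.2 points | 3 of 5 (6 points) |
| 0.96 | 2 | 4 points | 2.8 points | 2 of 2 (4 points) |

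**4. Median time.** The documents give no recovery times, so these are illustrations. Assume T_A is normal with SD 3 days, and T_P = T_A + a normal lag. The largest possible shift arises when every patient's platelet criterion is already met at ANC recovery: median(max(T_A, T_P)) − median(T_A). By simulation with 2,000,000 draws:

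| Mean lag of platelets behind ANC | Largest shift, lag SD 3 days | Largest shift, lag SD 5 days |
|---|---|---|
| −5 days (platelets first) | 0.05 day | 0.3 day |
| 0 days | 1.1 days | 1.6 days |
| 3 days | 3.1 days | 3.4 days |
| 7 days | 7.0 days | 7.0 days |

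Only upper bounds are given. Intermediate values depend on how soon a transfused count crosses 20,000. Take the 7-day lag with SD 3, and suppose a quarter of patients are already above 20,000 at ANC recovery. The shift is 1.7 days if the others wait for full unsupported recovery, but 5.5 days if a transfused count may cross within 2 days of ANC recovery. The documents do not allow a choice between these.

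**5. What is not touched.** DFS (12.4) runs to relapse or death. The 12.3 rule counts severe treatment-related complications and regimen-related mortality. Neither uses the engraftment date. The worst-case standard error behind n = 50 is √(0.25/50) = 0.0707 under either definition. The value 0.7 printed in 12.2 is a separate matter.

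**The case against.** The strongest case is that little depends on this. Engraftment is not among the objectives and is neither the primary nor a named secondary endpoint. No test, comparator or stopping decision uses it. The size is unknown, and the range includes no effect at all. Section 6.4 is a recommendation, so the effect also depends on adherence and on counts actually staying above 20,000. All of this stands, and it limits the weight of the point.

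Three further arguments stand only in part.

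- **Section 10.1 and the IBMTR booklet might supply the rule.** The 10.1 sentence is incomplete and the booklet is unseen, so their silence is weak evidence. Even so, 12.4 is the operative analysis definition, and it lacks the condition.
- **Section 12.4 may describe two milestones, not one joint event.** That would change how the rate and the median are computed. It does not remove the gap, because a transfused count would still meet the platelet milestone.
- **The citations of the CTC are general.** True. They show only that the CTC grades transfusion support without linking it to an engraftment date.

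A reader might also infer that the platelet criterion is empty, so that everyone supported under 6.4 counts as engrafted. The documents do not support that. A patient without ANC recovery still fails. So does a patient whose count stays below 20,000 despite transfusion, and the CTC itself names "platelet transfusion refractoriness associated with life-threatening bleeding".

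**Conclusion.** The gap is real and should be closed. As written, 12.4 lets donor platelets count as platelet recovery, so the engraftment rate may be overstated and the median time understated. More patients would not correct this error.

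The size cannot be estimated from the documents. The effect on the rate may well be small: to exceed one standard error, 3 of 10, 3 of 5 or 2 of 2 non-engrafted patients would have to be misclassified at assumed true rates of 80%, 90% and 96%. The median could be early by anything from nothing to about a week, depending on an assumed lag between ANC and platelet recovery.

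A reader might infer that the sample size or the efficacy result is compromised because 12.2 cites the engraftment rate. That does not follow. The worst-case precision at n = 50 is the same under either definition, and neither DFS nor the stopping rule uses engraftment. The point concerns descriptive engraftment estimates only.

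**What to change.** In 12.4, with matching wording in 10.1, state that the platelet count > 20,000 must be unsupported by transfusion for an interval that the investigators prespecify. Report ANC recovery and platelet recovery separately as well as combined. Take platelet transfusion dates from the chart, because the CTC transfusion item records a grade and not dates. The IBMTR booklet may reduce this work if it already collects them.

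The transfusion policy and the sample size do not change.

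The cost is a wording amendment and modest chart abstraction. Dating will be less precise after discharge: 6.4 specifies daily counts only in hospital, and the Appendix VI calendar moves from Day 7 to Day 100. The reported engraftment figure may come out later or lower.

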
FTBI and VP-16 in an attempt to decrease the relapse rate in those patients transplanted for advanced hematological malignancies. The rationale behind the study was that we combined three non-cross resistant anti-leukemic agents with non-overlapping extramedullary toxicities. An in vitro synergy has been demonstrated between busulfan/VP-16 and busulfan/VP-16 has been proven to be an effective regimen for relapsed leukemia and for ABMT for AML in first and second remission.^{23,24} The dose limiting toxicity occurred at 12mg/kg the MTD was defined at 11mg/kg. At this dose level median first dose AUC for these patients was 892 μ M*min (460-1267). With a median follow-up of 11.5 months, the disease-free survival is 32%, and the probability of relapse is 40%. The only variable predictive of a disease-free survival and relapse was the busulfan dose of 7-8 mg/kg. In this phase I study there was a wide variability of the AUC of busulfan due to the variability of absorption of oral busulfan. An AUC of 700-950 showed a trend to a decreased relapse rate and improved disease free survival.

A phase II study utilizing IV busulfan was conducted at City of Hope which has resulted in FDA approval of IV busulfan and it is proposed to substitute IV busulfan which has been shown to have more predictable pharmacokinetic properties than the oral preparation resulting in a better toxicity profile.^(25,26,27)

Rev. 6/13/02

*Patients with AML in first complete remission (CR1) with unfavorable cytogenetics have a relapse rate of 40% with our current transplant regimen consisting of fractionated radiation and etoposide. We propose to use this new preparative regimen to see if it can improve the DFS and relapse rate for this subset of patients with AML in first CR.

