5.0 ELIGIBILITY CRITERIA

5.1 Inclusion Criteria

- 5.1.1 Patients with acute myelogenous or lymphocytic leukemia who are not in first remission or second remission i.e. after failing remission induction therapy or in relapse or beyond second remission, or patients with chronic myelogenous leukemia in blastic phase of the disease are eligible for the study. Patients with refractory anemia with excess blasts and in transformation will be eligible.
- 5.1.2 All candidates for this study must have a HLA (A,B,C,DR) identical siblings who is willing to donate bone marrow for marrow grafting. All ABO blood group combinations of the donor/recipient are acceptable since even major ABO compatibilities can be dealt with by various techniques. (Red cell exchange or plasma exchange). Peripheral blood stem cells or bone marrow can be used.
- 5.1.3 Prior therapy with VP-16 and busulfan is allowed.
- 5.1.4 Patients must be older than 16 and the upper age limit is physiological age of 50.
- 5.1.5 A cardiac evaluation with electrocardiogram and MUGA or echocardiogram is required in all patients. Patients must have an ejection fracture of greater than or equal to 50%.
- 5.1.6 Patients must have a serum creatinine of less than or equal to 1.2 or creatinine clearance $> 80\text{ml/min}$.
- 5.1.7 A bilirubin of less than or equal to 1.5. Patients should also have an SGOT and SGPT less than 5 times the upper limit of normal.
- 5.1.8 Pulmonary function tests including DLCO will be performed. FEV₁ and DLCO should be greater than 50% of predicted normal value.

5.1.9 The time from the last induction or reinduction attempt should be greater than or equal to 28 days.

5.1.10 Signed informed consent form approved by the IRB is required. The patient, family member and transplant staff physician (physician, nurse, and social worker) meet at least once prior to starting the transplant procedure. During this meeting all pertinent information with respect to risks and benefits to donor and recipient will be presented. Alternative treatment modalities will be discussed. The risks are explained in detail on the enclosed consent forms.

Revised 8/28/00

Revised 3/11/02

Revised 6/13/02

5.1.11 Patients with AML in first remission with poor risk cytogenetics (11q abnormalities, -7,-5, complex abnormalities i.e. > 3 abnormalities, 6;9 translocation and 3q abnormalities del (7q), del (5q), complex abn ≥ abnormalities, 9q, 20q, 21q, 17p, t(9;21)).

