The intent-to-treat group will include all patients receiving the preparative regimen for BMT. For overall survival, failure time will be calculated from the day of first treatment to the day of death due to any cause for those patients who fail. For DFS, the failure time will be calculated from the day of first treatment to the day of disease relapse or death due to any cause. For patients who remain alive and well at the time of analysis, the survival time will be censored as of the date of last contact. The Cox proportional hazard regression model will be used to analyze possible prognostic factors for relapse, DFS and overall survival.

Revised
9/26/00

12.5 Patients with AML with unfavorable cytogenetics will be a subset analysis that will include approximately 12 patients. This number is too small for formal hypothesis testing. It will give us some experience with this population of patients and descriptive analysis will be used along with estimation of relapse rate and 95% C.I.

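### Section 12.4 plans Kaplan-Meier for time to relapse without saying how death without relapse is handled; if such deaths are censored, the relapse probability is overstated

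*Combined protocol and SAP*

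**What the plan says.** Section 12.4 of the combined protocol and SAP states: "The Kaplan-Meier method will be used to estimate time to relapse, DFS, and overall survival". The 95% intervals use Greenwood's variance.

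The section then gives the start and the event for two of these three outcomes. Overall survival runs from first treatment to death. DFS runs from first treatment "to the day of disease relapse or death due to any cause". The only censoring sentence is "For patients who remain alive and well at the time of analysis, the survival time will be censored" (at last contact). That can cover survivors who have not relapsed. It does not cover patients who die without relapse.

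A Cox model is planned for relapse, DFS and overall survival. Section 10.4 defines a composite treatment failure (toxic death or recurrence), which does not settle the relapse analysis. For the subset of about 12 AML patients with unfavorable cytogenetics, section 12.5 says "descriptive analysis will be used along with estimation of relapse rate and 95% C.I" and names no estimator. Neither cumulative incidence nor competing risks is mentioned anywhere.

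**The concern.** Relapse is listed separately from DFS, and DFS already counts death. If death also counted as an event in the relapse analysis, the two curves would be the same. What remains is that deaths without relapse are censored. The plan does not say this, so it is an inference.

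Kaplan-Meier treats a censored patient as still able to have the event later. A patient who has died cannot relapse. One minus the curve then describes relapse in a population where nobody dies of anything else, not the share of transplanted patients who relapse.

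Relapse is not a named endpoint, and no test or stopping rule uses it. It is still a planned result that matters here:

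- Section 2.0 says the preceding phase I study added busulfan "in an attempt to decrease the relapse rate in those patients transplanted for advanced hematological malignancies", and gives a better relapse rate as an aim in first-remission AML.
- Section 12.2 justifies the 50 patients by the precision of the engraftment and relapse rates.

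The overstatement grows with the number of early toxic deaths, so toxicity would be mixed into the efficacy figure that the regimen is meant to improve.

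**Working it through.** **1. The plan's own precision figure.** Section 12.2 prints a maximum standard error of 0.7 for the relapse rate with 50 patients. For a proportion the maximum is √(0.5 × 0.5 / 50) = 0.071, so the printed value looks like a decimal slip for 0.07. The point here does not depend on it, but 7 points is the yardstick used below.

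**2. Direction.** Let A(t) and B(t) be the cumulative hazards of relapse and of death without relapse, and a(t) the relapse hazard.

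- One minus Kaplan-Meier with deaths censored targets ∫ a(t) exp(−A(t)) dt.
- The actual relapse probability (cumulative incidence, CIF) is ∫ a(t) exp(−A(t) − B(t)) dt.

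Since B(t) ≥ 0, the first is never smaller. They are equal only if no deaths precede relapses.

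**3. Size with a constant ratio of hazards.** Inputs:

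- Kaplan-Meier relapse R of 40-70%. This is the background range in section 2.0, taken as Kaplan-Meier figures (assumption).
- Non-relapse mortality (NRM) of 5-30% (assumption). The 20% in section 12.3 ("regimen related mortality exceeds 20% with a high probability") is a monitoring level, not an expected rate.

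Method: a = −ln(1 − R); solve for b in b/(a+b) × [1 − exp(−(a+b))] = NRM; then CIF = a/(a+b) × [1 − exp(−(a+b))].

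Example, R = 0.40 and NRM = 0.20: a = 0.511, b = 0.291, CIF = 0.351, gap = 0.400 − 0.351 = 4.9 points.

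Gap R − CIF, in percentage points:

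| NRM | R = 40% | R = 50% | R = 60% | R = 70% |
|---|---|---|---|---|
| 5% | 1.2 | 1.6 | 2.0 | 2.4 |
| 10% | 2.4 | 3.1 | 4.0 | 4.9 |
| 20% | 4.9 | 6.4 | 8.1 | 10.1 |
| 30% | 7.5 | 9.8 | 12.4 | 15.5 |

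**4. Limits by order of events.** If all relapses come first, the gap is 0. If all deaths come first, CIF = R × (1 − NRM), so the gap is R × NRM. For R from 40% to 70% that is 2.0-3.5 points at 5% NRM, 4-7 at 10%, 8-14 at 20% and 12-21 at 30%.

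**5. Coverage of the planned 95% interval.** Simulation with 50 patients, 40,000 replicates, exponential relapse, complete two-year follow-up and a linear Greenwood interval at two years. The target is the actual relapse probability.

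| Setting | R = 40% | R = 60% |
|---|---|---|
| NRM 5%, constant hazard | 94% | 93% |
| NRM 10%, constant hazard | 93% | 90% |
| NRM 20%, constant hazard | 90% | 80% |
| NRM 30%, constant hazard | 85% | 66% |
| NRM 10%, all deaths by day 100 | 92% | 86% |
| NRM 20%, all deaths by day 100 | 84% | 67% |

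The same interval covers its own Kaplan-Meier target about 94% of the time. A cumulative incidence (Aalen-Johansen) interval covers the actual probability about 94% of the time in the constant-hazard cases.

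**6. The phase I figures as illustration.** Section 2.0 reports DFS of 32% and a relapse probability of 40%, here taken at the same time point.

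- If the 40% is a cumulative incidence, NRM = 100 − 32 − 40 = 28%. The relapse share of failures is 0.40/0.68 = 0.588, and one minus Kaplan-Meier is 1 − 0.32^0.588 = 48.8%, an excess of 8.8 points. With deaths first it is 0.40/0.72 = 55.6%, an excess of 15.6.
- If the 40% is itself one minus Kaplan-Meier, the share is ln 0.60/ln 0.32 = 0.448 and CIF = 0.448 × 0.68 = 30.5%, so the printed figure is 9.5 points too high. NRM is then 100 − 32 − 30.5 = 37.5%.

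That study escalated oral busulfan and had a median follow-up of 11.5 months. It shows that the upper part of the assumed mortality range is plausible; it is not a forecast.

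**7. The 12-patient subset.** The standard error is up to √(0.25/12) = 14 points. Beside that, a gap of 2.4-4.9 points (R = 40%, NRM 10-20%) is minor.

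**The case against.** **The bias needs two things the plan does not state:** that deaths are censored, and that one minus the curve is reported as the relapse probability. Sections 12.2 and 12.5 speak of a relapse rate, and the 12.2 precision (read as 0.07) matches a simple proportion, which with complete follow-up would have no such bias. This lowers certainty about what would be reported. It does not remove the point: a Kaplan-Meier relapse curve with Greenwood intervals is ordinarily read as a probability, and the plan is silent on these deaths either way.

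**The practical effect is limited.** The study is single-arm and estimates only. DFS (the efficacy measure), overall survival, the stopping rule and a cause-specific Cox model are untouched. At 40-50% relapse and up to 20% mortality, the constant-hazard gap is below one standard error. All of this stands.

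**Some scenarios fit the protocol poorly.** R = 40% with NRM of 5% or 20% implies DFS of 100 − 38.8 − 5 = 56% or 100 − 35.1 − 20 = 45%, above the 10-40% success range that section 2.0 gives for advanced disease. This is fair, but it weakens the small gaps rather than the large ones. The phase I figures also allow mortality of 37.5%, above the assumed range.

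**The remedy could go beyond the defect.** A rule for patients who never reach remission, and a label on the Cox model, supply missing detail and are not needed to remove this bias. That is accepted; they are worth settling in the same edit.

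**Conclusion.** The concern holds. The plan gives no rule for death without relapse in its Kaplan-Meier relapse analysis. Under the natural reading (deaths censored, one minus the curve reported), the relapse probability is never understated and is overstated whenever such deaths precede later relapses.

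The size rests on assumed mortality and on timing. It is small if non-relapse deaths are few or late. At 20% or more mortality with 60-70% relapse and a constant hazard ratio, it exceeds one standard error, and interval coverage at 60% relapse falls to about 80% or lower. The result at stake is secondary, so the plan should be corrected, but its main efficacy conclusion is not in question.

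**What to change.** In section 12.4:

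- Estimate relapse by cumulative incidence (Aalen-Johansen, with matching variance and 95% interval) from the day of first treatment. Treat death without relapse as a competing event, and censor patients alive and relapse-free at last contact.
- Report non-relapse mortality in the same way.
- Keep Kaplan-Meier with Greenwood intervals for DFS and overall survival, and state that the Cox model for relapse is cause-specific.
- Say how patients who never reach remission are counted, with the same rule for relapse and DFS. Section 5.1.1 enrols patients "after failing remission induction therapy or in relapse or beyond second remission", while section 10.2 says "Complete remission is defined as attainment of M-1 marrow status".
- Add a supplementary Kaplan-Meier relapse figure, labelled as such, for comparison with historical results.

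Use the same relapse estimator in section 12.5.

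The cost is wording and a standard procedure; no new data are needed. The one drawback is that the main relapse figure is less directly comparable with historical figures if those were Kaplan-Meier estimates. The supplementary figure meets that.
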